4.3.2.7.3 Pump Bolus Occlusion Alarms

of pump bolus occlusion alarms will be counted for each day.

4.3.2.7.4 Pump Basal Occlusion Alarms

of pump basal occlusion alarms will be counted for each day.

4.3.3 Safety Variables

4.3.3.1 Device Malfunctions

4.3.3.1.1 Hyperglycemia (Glucose >250 mg/dL) not Responsive to Correction Bolus

This hyperglycemia episode is reported by the investigational site. Occurrence of these cases will be counted. A subject without any reported cases will have a count of 0.

4.3.3.1.2 Hyperglycemia with Elevated Ketones (Glucose >250 mg/dL and a Ketone Value ≥ 0.6 mMol/L) in the Absence of Evidence of Intercurrent Illness.

This hyperglycemia episode is reported by the investigational site. Occurrence of these cases will be counted. A subject without any reported cases will have a count of 0.

4.3.3.1.3 Evidence of Infection or Clinically Meaningful Inflammation at the Infusion Site

This is reported by investigational site and the occurrence of these cases will be counted. The number of hours following cannula insertion will be reported for each occurrence. A subject without any reported cases will have a count of 0.

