Secondary Endpoints 4:	
 • Proportion of investigational CSII sets that did not fail on each day of use. • Mean difference across treatments in time to device failure • Mean difference across treatment in incidence of pump bolus occlusion alarms • Mean difference across treatment in incidence of pump basal occlusion alarms

Safety Objectives:	To assess Achilles infusion set safety and tolerability from DOI through day 7 for each treatment
Safety Endpoints:	
 • The occurrence hyperglycemia (glucose >250 mg/dL) not responsive to a pump bolus dose where response to the bolus is defined as a fall of at least 50 mg/dL in blood glucose within one hour, • The occurrence of hyperglycemia (glucose >250 mg/dL) after prolonged fasting (e.g. overnight or more than 5 hours following a meal), not associated with acute intercurrent illness, but with a concurrent ketone level ≥ 0.6 mmol/L. • Localized infection or inflammation of greater than 1.0 cm in diameter at the infusion site • Occurrence of an insulin pump occlusion alarm signal • Cannula dislodgement from subcutaneous space, • Cannula malfunction (inability to pierce skin, bending, kinking, fluid leakage or other malfunction that might impact insulin infusion) • Mean visual analog scores (VAS) scores (0-100 mm) from Day of insertion through Day 7 of use • Mean difference of VAS scores (0-100mm) of CSII investigational sets and CSII control sets • Descriptive statistics of per subject term, severity, adverse device effects, and frequency of adverse events for each treatment • Descriptive statistics of per subject incidence of unanticipated adverse device effects
Study Population:	
Up to 30 adult participants, with the goal of having approximately 24 completers, may be enrolled, ages 18–70, diagnosed with Type 1 diabetes mellitus (T1DM) who have ≥ 6 months experience using rapid-acting insulin analog delivered via Medtronic MiniMed insulin pump and infusion sets. Only Medtronic pump models 530 and higher may be used.
 
Study participants will be drawn from existing T1DM patient populations meeting the study eligibility at each study center and from referral practices.

Phase:	Phase 1b
Description of Sites /Facilities Enrolling Participants:	This study will be conducted at no more than 5 centers in the United States. Each site will be qualified to conduct insulin treatment studies per a standardized euglycemic clamp protocol.

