4.1 OVERALL DESIGN

This is an open, single-center, 2-way randomized, cross-over trial investigating the survivability, consistency, efficacy, and safety of an extended wear time investigational insulin infusion set (CapBio Achilles). This is achieved by measuring PK and PD profiles of a bolus of rapid acting insulin on 4 separate days of CSII set wear time during 2 separate wear periods in up to 30 adult patients with T1DM.

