6.1.1.9 ANCILLARY PRODUCTS AND ACCESSORIES

During Visit 0, Participants will be provided with diabetes diaries and a bag of material for times spent at home in between study visits to the CRU.

Contents of bag:

- Achilles infusion set change out and device return instructions
- Glucose meter (handling is explained by study staff)
- Ketone meter (handling is explained by study staff)
- Glucose strips
- Ketone strips
- Glucose tabs
- Diary

- Cap for infusion set (in case of failure)
- Ruler/Cutout to measure erythema
- Container & biohazard bag for CSII catheter (in case of failure)
- Alcohol swabs

Study sponsor shall provide the following study materials and products for study use only:

- Dexcom G6® CGM
- Fast-acting insulin (Insulin Lispro U100/Humalog)
 - **NOTE:** Participants who are using other pump insulins will be switched to lispro after screening and informed consent to participate have been completed.

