7 DISCONTINUATION AND WITHDRAWAL

7.1 DISCONTINUATION OF STUDY INTERVENTION

7.1.1 INFUSION SET CHANGE-OUT/EARLY DROPOUT

Independent of the time point for infusion set removal/change out, study staff is to follow the SOP for Infusion Set Removal and the reason for change-out is to be documented in the applicable source document and CRF.

We anticipate several commercial and/or investigational CSII catheters to fail prior to the fourth glucose clamp experiment on day 7. Participants will be instructed to contact the research investigator by telephone (24/7) to confirm the diagnosis of a failed CSII catheter. If the CSII catheter does not fail before day 7, the investigational/commercial CSII set will be removed upon completion of the clamp experiment on Visit 4A/Visit 4B. The site and cannula will be photographed, and the cannula inspected under a microscope.

The following are objective criteria that define a CSII catheter/infusion set failure:

1. The occurrence hyperglycemia (glucose >250 mg/dL) not responsive to a pump bolus dose where response to the bolus is defined as a fall of at least 50 mg/dL in blood glucose within one hour.
2. The occurrence of hyperglycemia (glucose >250 mg/dL) after prolonged fasting (e.g. overnight or more than 5 hours following a meal), not associated with acute intercurrent illness, but with a concurrent ketone level ≥ 0.6 mmol/L.
3. Signs of inflammation/infection at the infusion site including pain, erythema or induration >10 mm in diameter.
4. Occurrence of an insulin pump occlusion alarm signal.

In the case that any of the above occurs during home-use, the participant is asked to call the 24/7 helpline and confirm catheter failure with the study staff. The study participant will insert a new commercial CSII catheter (as used routinely by this patient) into the subcutaneous tissue at an alternate location and connect it to the insulin pump for routine glycemic management. The failed CSII catheter will be left in place. The participant is asked to measure erythema around the catheter and photograph the site. The study participant will return to the study site as soon as practicable so the research staff can remove and observe the failed CSII catheter. Study staff is to follow the SOP for catheter removal.

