4.4.5.4 Device Malfunctions

Device malfunctions as specified in section 4.3.3.1 will be presented descriptively

Population	Safety
------------	--------

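### The SAP counts infusion-site reactions by an undefined clinical-meaningfulness judgement instead of the protocol's cut-off of more than 1.0 cm, and does not declare the change

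*SAP*

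**What the plan says.** **Protocol.** The synopsis names the safety endpoint as "Localized infection or inflammation of greater than 1.0 cm in diameter at the infusion site". Section 7.1.1 uses the same size among the criteria it calls objective for declaring a set failed: "Signs of inflammation/infection at the infusion site including pain, erythema or induration >10 mm in diameter". Section 2.3.3 places site irritation or infection among the primary risks of extended Achilles wear. Section 4.1 describes the design: "This is an open, single-center, 2-way randomized, cross-over trial".

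**Data collection.** The home kit includes a "Ruler/Cutout to measure erythema" (6.1.1.9). When a failure criterion occurs during home use, 7.1.1 adds: "The participant is asked to measure erythema around the catheter and photograph the site". The schedule of activities has the site evaluated at each clamp visit and daily during wear, and photographed by staff at insertion and at the end of each wear period. Section 6.4 makes photographs the source document for site reactions.

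**SAP.** Section 4.3.3.1.3 is headed "Evidence of Infection or Clinically Meaningful Inflammation at the Infusion Site" and states: "This is reported by investigational site and the occurrence of these cases will be counted". A subject with no reported case scores 0. Section 4.4.5.4 gives the analysis: "Device malfunctions as specified in section 4.3.3.1 will be presented descriptively". Section 2.5, which lists modifications from the protocol's statistical section, mentions only the consequences of early termination.

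**The concern.** The protocol endpoint is the occurrence of a reaction above a stated size. The SAP variable is the occurrence of a reaction that someone considers important. These are different events, and the second has no written rule that two assessors could apply alike.

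This matters for two reasons. The endpoint covers one of the main risks the protocol attributes to wearing the investigational set for longer. And staff know which set was worn: a numeric limit restricts how far that knowledge can shape the call, while an undefined judgement does not. A reader of the final report would see a site-reaction count by set and could not tell whether it answers the protocol's question.

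**Working it through.** The plan states no figure for this endpoint, so there is nothing to reproduce. The check compares the texts, with one unit conversion and one scale calculation.

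**1. Do the protocol's own limits agree?** 1.0 cm = 10 mm. The synopsis endpoint and failure criterion 3 in 7.1.1 use the same limit, and the SAP variable uses neither.

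**2. Is the omission just the SAP's shorthand?** Both hyperglycemia variables immediately before it keep the glucose limit of 250 mg/dL in their headings, and the second also keeps the ketone limit of 0.6 mmol/L. The first does not repeat the protocol's response rule (a fall of 50 mg/dL within one hour), so the SAP does abbreviate in places. For site reactions, however, the number is replaced by a different, qualitative criterion.

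**3. Is the limit restored elsewhere in the SAP?** No. The failure definition in SAP 4.3.2.7.1 names site infection but neither inflammation nor a size. Section 2.5 does not mention the change.

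**4. What happens to individual reactions?**

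| Reaction | Protocol safety endpoint | SAP 4.3.3.1.3 | SAP failure definition (site ground) |
|---|---|---|---|
| Not infected, over 1.0 cm, staff think it unimportant | Event | 0 | Not met |
| Not infected, over 1.0 cm, staff think it important | Event | Counted | Not met |
| Not infected, 1.0 cm or less, staff think it important | No event | Counted | Not met |
| Infection of 1.0 cm or less | No event, if the size applies to infection as well as inflammation | Counted | Met |

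The first row is the loss. The third and fourth show that the SAP rule can also add events, so the direction of the net change is not known.

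**5. How much can one judgement move?** Assume seven wears per set, since SAP 2.5 says the study was stopped after the seventh subject completed. One participant moved across the boundary changes a set's incidence by 1/7 = 14.3 percentage points. Exact 95% intervals (Clopper-Pearson):

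- 0/7 = 0% (0 to 41.0%)
- 1/7 = 14.3% (0.4 to 57.9%)
- 2/7 = 28.6% (3.7 to 71.0%)

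The Safety population may exceed the seven completers, and its size is not given. At the protocol's ceiling of 30 participants the step would be 1/30 = 3.3 points. These figures show scale only; they do not estimate bias.

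**The case against.** The case against making much of this has real content.

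- **The reaction need not disappear.** Protocol 8.3.5 requires local reactions and all adverse events to be captured on the CRF whatever their severity. SAP 4.4.5.1 lists adverse events, or summarises them by treatment with intensity and device-related subgroups. Protocol 7.1.1 also has the reason for a change-out recorded. This stands: the loss is to the named endpoint, not necessarily to the record.
- **Sites may already apply the 10 mm limit when they report.** Possible, but the SAP neither says so nor points back to the protocol.
- **Nothing inferential depends on it.** The variable is only described, with no test, and the intervals above are very wide. This stands, and it limits the importance of the point.

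A reader might also infer more than the documents support:

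- *That a set of recorded diameters is being left unanalysed.* Measurement is requested only from the participant, when a failure criterion occurs at home. Daily home checks are visual (Table 7), planned removal on day 7 calls for a photograph, and no diary or CRF field for diameter is described. Protocol 9.4.4 plans no diameter analysis. What the SAP drops is the cut-off. Its list of outputs is a separate file that was not available, so statements about omitted analyses can cover the SAP text only.
- *That the SAP introduced unmasked assessment.* The open design did, and it applies equally to the protocol's endpoint. The SAP adds discretion to an assessment that was already open.

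**Conclusion.** The point holds in a limited form. SAP 4.3.3.1.3 substitutes an undefined, site-reported judgement for a protocol safety endpoint with a stated size limit, and the SAP does not declare it. A non-infectious reaction over 1.0 cm can therefore score 0 on the endpoint meant to capture it and fall outside the SAP failure definition too, while possibly appearing among the adverse events.

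The effect cannot be sized. The documents contain no reaction rates and nothing on how sites would use the term. The 14.3-point step per participant rests on the assumption of seven wears per set. It would be tempting to conclude that the comparison between sets will be biased in one direction, but nothing in the documents shows that staff would judge the two sets differently, and the SAP rule can add events as well as remove them. The correction is still worth making: the mismatch is clear, it touches a primary named risk, and removing it is cheap.

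**What to change.** 1. In SAP 4.3.3.1.3, count events using the protocol endpoint's own wording and its cut-off of more than 1.0 cm. Apply the rule identically to both sets, from the scheduled site evaluations, the photographs and any measurement taken.
2. Keep the site's judgement of clinical meaningfulness as a supplementary listing.
3. Declare any departure that remains, with a reason, in SAP 2.5.
4. Reconcile the site-reaction part of the failure definition in SAP 4.3.2.7.1 with protocol 7.1.1. This concerns consistent counting; it proposes no rule for when a set should be removed.
5. List diameters where they were measured, but do not compare maximum diameter between sets. Measurement is requested only when a set fails at home, so sets that reach day 7 would be systematically missing.

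**Cost.** SAP wording and reclassification of one descriptive variable. More mild reactions may be counted on both sets. Where no measurement exists, some wears may have to be classified from photographs, which takes some effort and leaves some uncertainty near the limit.

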4.3.3.1.4 Cannula Dislodgement

It is reported by investigational site and the occurrence of these cases will be counted. A subject without any reported cases will have a count of 0.

4.3.3.1.5 Cannula other Malfunctions

It is reported by investigational site and the occurrence of these cases will be counted. A subject without any reported cases will have a count of 0.

4.3.3.2 Visual Analog Scale (VAS) for Pain Assessment

The VAS score will be normalized to 100 mm based on the reported pain score length and the total line length.

The mean VAS score of each subject is calculated as:

$$\text{Mean VAS} = \frac{\text{Sum of (all available VAS Score)}}{\text{\# of all available VAS Score}}$$

4.3.3.3 Exposure (h) to Study Device

The exposure of the device will be in days and calculated as:

The date/time of last device removal – the date/time of first device insertion

It will then be transformed to hours.

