9.4.4 SAFETY ANALYSES

Tolerability of infusion sets will be assessed by comparing the mean VAS scores from day of insertion through Day 7 of use with a mixed-effects (repeated-measures) linear model with treatment, period and day as fixed effects and participant as a random effect. The mean difference between treatments will be compared with a two-sided test using significance level $\alpha=0.05$.

Adverse events (AEs) will be coded using CTCAE v4.0. Descriptive statistics (number of participants and per-participant incidence) for device-related AEs will be presented by System Organ Class, Preferred term, severity and treatment. Unanticipated and serious device-related AEs will be presented separately by treatment.

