4.2.6 Unexpected switch of the infusion set

Anytime when the participant switched the use of the study infusion set to other infusion set, it is considered the study infusion set is removed for the corresponding period regardless if the study infusion set is used again or not.

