4.4.2 General Consideration of Descriptive Summary

The following rules will be used, unless specific described, for any descriptive summary.

1. Descriptive summary will be by treatment and by period
2. For continuous variables: mean, SD, median, minimum and maximum will be reported. Two decimal points will be used unless specified.
3. For category variables: count, percentage, and the total used as a denominator will be reported. One decimal point will be used unless specified.

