4.4.5 Safety Analysis

4.4.5.1 Adverse Events

Adverse events will be listed only if the total # of AE in the whole study is less than 5.

Otherwise, they will be summarized by presenting, for each dose/treatment group, the number and percentage of participants experiencing any adverse event, experiencing an adverse event in each system organ class (SOC) and experiencing each individual adverse event.

- If two events of the same symptom of the same subject happens within 5 minutes, it will be considered as a single event in the summary.

Subgroups of intensity and subgroups of device-related tables should also be presented.

Any other information collected (e.g. severity or relatedness to study medication) will be listed as appropriate.

Population	Safety
------------	--------

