4.4.5.5 Exposure to Study Device

Participant exposure to study device will be presented descriptively

Population	Safety
------------	--------

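### SAP 4.3.3.3 defines device exposure without naming the set, treatment or period, and adverse event and malfunction tables have no wear-time denominator

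*SAP*

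**What the plan says.** - **Exposure.** SAP 4.3.3.3 derives it as "The date/time of last device removal – the date/time of first device insertion", converted to hours. SAP 4.4.5.5 adds only that "Participant exposure to study device will be presented descriptively".
- **Default unit for summaries.** SAP 4.4.2 states that "Descriptive summary will be by treatment and by period", unless a section says otherwise.
- **Switching sets.** Under SAP 4.2.6, once a participant moves to another set "it is considered the study infusion set is removed for the corresponding period".
- **Failed sets at home.** Protocol 7.1.1 has the participant insert a routine set elsewhere. It adds: "The failed CSII catheter will be left in place". Staff remove the failed catheter at a later visit, with no interval given.
- **Adverse events.** SAP 4.4.5.1 reports "the number and percentage of participants experiencing any adverse event", or only a listing if there are fewer than five events in the study. Protocol 9.4.4 plans "Descriptive statistics (number of participants and per-participant incidence) for device-related AEs". Protocol 8.3.4 collects events continuously through the study.
- **Malfunctions.** SAP 4.3.3.1 counts occurrences: "A subject without any reported cases will have a count of 0". SAP 4.4.5.4 presents the counts descriptively.

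**The concern.** Each participant wears two different sets, separated by a 7-21 day washout. A formula that runs from the first insertion to the last removal, with no unit named, can be programmed once per participant. The result would include the washout and could not be attributed to either device. Even within one period, the recorded removal of a failed set can come after the participant has stopped using it.

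The exposure table matters because wear is expected to be unequal: a period ends at change-out, and the protocol plans for 40-50% failures. The safety objective concerns tolerability over extended wear. Yet a participant whose set came out on day 1 without a reported event enters the malfunction table as a zero, exactly like one who wore the set for seven days. For events that can occur repeatedly without ending wear, the set worn longer has more time to accrue them. No planned adverse event or malfunction table shows how much time each set was at risk.

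**Working it through.** The documents state no exposure or event-rate figure, so there is nothing to reproduce. Three checks follow.

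**1. Span of the exposure formula**

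Inputs: up to 7 days' wear in each of two periods (SAP 3.3.1); washout of 7-21 days (Protocol 1.1).

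- Once per participant: 7 + 7 + 7 = 21 days (504 h) to 7 + 21 + 7 = 35 days (840 h).
- Maximum wear of both sets: 14 days (336 h). Ratios: 504/336 = 1.5 and 840/336 = 2.5.
- By treatment and period: one set's insertion-to-removal time, at most about 168 h, which is close to wear.

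**2. Failed sets timed to physical removal**

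With constant hazard, a failure proportion f by day 7 gives hazard h = -ln(1 - f)/7 and mean wear f/h.

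- f = 0.40: mean wear 5.48 days (131.6 h).
- f = 0.50: mean wear 5.05 days (121.2 h).

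If removal follows the switch by d hours, mean exposure is overstated by f × d. The documents do not give d, so these values are assumptions:

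| d | f = 0.40 | f = 0.50 |
|---|---|---|
| 24 h | 9.6/131.6 = 7% | 12/121.2 = 10% |
| 48 h | 19.2/131.6 = 15% | 24/121.2 = 20% |

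The excess arises only for failed sets, so it is larger for the device that fails more often.

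**3. Unscaled counts**

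*Events that do not end wear.* At equal daily risk, the ratio of expected counts equals the ratio of mean wear. Achilles survival is an assumption, because the documents give no figure.

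- Control at 40-50% failure (Protocol 9.4.1), every Achilles set worn 7 days: 7/5.48 = 1.28 to 7/5.05 = 1.39.
- Same control, with 20% Achilles failure (mean wear 6.27 days): 6.27/5.48 = 1.14 to 6.27/5.05 = 1.24.
- Control on the Teflon curve cited in Protocol 2.2.3 (85, 77, 59, 46 and 33% functioning at days 1, 3, 5, 6 and 7), by trapezoid: 0.925 + 1.62 + 1.36 + 0.525 + 0.395 = 4.83 days. With full Achilles wear, 7/4.83 = 1.45.

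For illustration, take an assumed 0.1 events per day and 7 participants, with wear of 7.0 against 4.83 days. Expected counts are 7 × 0.1 × 7.0 = 4.9 against 7 × 0.1 × 4.83 = 3.4. Participants with at least one event would be 1 - exp(-0.70) = 50% against 1 - exp(-0.483) = 38%. Scaled, both sets show 10 per 100 set-days.

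*Events that end wear.* Assume 20% against 45% failure by day 7. Raw counts per 7 participants are 1.4 against 3.2 (7 × 0.20 and 7 × 0.45). Rates per 100 set-days, 100 × h, are 3.2 against 8.5. Both measures favour the set that lasts longer.

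**The case against.** **The formula is already confined to one set.** Exposure is a descriptive summary, so SAP 4.4.2 splits it by treatment and period. Only one study set is worn to end of use in a period, and SAP 4.2.6 treats a switched set as removed. This largely stands: read together, the sections give nearly the right quantity, so a flat claim that the formula fails to measure wear would go too far. What remains is that 4.3.3.3 is the derivation, refers to neither section, and does not say whether the switch or the recorded removal supplies the end time.

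**A reader might infer that the longer-lasting set will look less safe overall.** The documents do not support that. Under Protocol 7.1.1, unresponsive hyperglycemia, hyperglycemia with ketones, site inflammation or infection above 10 mm, and an occlusion alarm (SAP 4.3.2.7.1 narrows this to a non-resolvable alarm) define set failure. Failure leads to change-out, and dislodgement ends use as well. A longer-lasting set would show fewer of these. Nor can equal daily risk of such events be combined with unequal survival, so the ratios of 1.3 to 1.45 do not apply to them.

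**The inputs could be picked high.** The cited Teflon curve comes from QuickSet, not the Silhouette control, and the protocol's Risk Benefit Statement says that it overstates expected control failure. The 1.45 is therefore an upper figure. Comparing the 21-35 day span with one set's 168 h would give 3 to 5 times, but that sets a two-set span against one set.

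**Time is not ignored.** Set failure has daily survival, time to failure, a life table and a log-rank test. Occlusion alarms are counted per day, and infection or inflammation events carry hours since insertion. This stands for failures. It does not supply a denominator for other events.

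**Adverse events need not track wear.** They are also collected during washout and after change-out, and the SAP has no rule assigning them to a device. This is correct, and it is a reason to state an attribution window.

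**Conclusion.** The point holds in limited form. SAP 4.3.3.3 omits its unit. The literal reading overstates total wear by 1.5 to 2.5 times if both sets run 7 days, but SAP 4.4.2 makes that reading avoidable. Timing failed sets to physical removal would still overstate their exposure, by an amount that depends on a delay the documents do not state.

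The missing wear-time denominator matters for events that do not end wear, such as minor site reactions and other device-related adverse events. At equal daily risk the distortion is up to about 1.3 to 1.4 times with 40-50% control failure and full Achilles wear, and less if some Achilles sets fail. It does not extend to events that are themselves failures.

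The safety tables concerned are descriptive, and the study stopped after 7 completers, so no test is affected. The consequence lies in how the tables are read.

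**What to change.** 1. In SAP 4.3.3.3, define exposure for each set within treatment and period. It is the earliest of confirmed failure, switch under 4.2.6, or removal, minus the insertion of that set. Sum it by treatment.
2. In SAP 4.4.5.1 and 4.4.5.4, keep the counts and percentages. Add events per 100 set-wear days by treatment for events that occur during wear, with this exposure as the denominator.
3. Report adverse events from the washout or after change-out separately.

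The cost is SAP wording, one derived variable and one extra table column. No new procedure is needed: SAP 4.3.2.7.2 and 4.3.3.3 already call for failure, insertion and removal times, and the protocol has change-outs documented on the CRF. With so few participants the rates will be imprecise, so they belong beside the counts and not in place of them.
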